9.4.1.2. Secondary Bactericidal Activity Analyses

EBA measures (BA_{CFU}(0-2) and BA_{CFU}(2-14)) will be calculated from the regression models and assessed similarly as described above for BA_{CFU}(0-14). MGIT TPP and concentrations of LAM will also be assessed similarly. For all secondary EBA measurements there will be no adjustment for multiple comparisons and no formal success criteria.

All efficacy analyses will be performed in the mITT population, with sensitivity analyses performed in the per-protocol population to assess the robustness of results.

One of the limitations of the primary analysis method is that each individual subject must have enough data to fit a bilinear regression model in order to be included in the primary analysis. More sophisticated statistical models, such as a Bayesian nonlinear mixed-effects regression model ¹³ do not have this same limitation, and will therefore be examined through sensitivity analyses to assess the robustness of the primary model fits. The Bayesian model jointly fits the data from all patients and treatment groups and comprises the joint bilinear regression model as a special case. In addition, similar bilinear and linear regressions will also be fit directly to the change from screening response variable to further assess the robustness of the results.

9.4.2. Safety Analyses

9.4.2.1. Primary Safety Analyses

The frequency of patients who experienced one or more severe AEs and/or SAEs will be summarized by treatment group with 95% CIs. The proportion of patients with this endpoint within each of the TBA-7371 treatment groups will not be formally compared to the control arm given limitations due to small sample sizes. The primary safety analysis will be performed in the Safety population.

9.4.2.2. Secondary Safety Analyses

Individual safety parameters of interest, e.g., mean HR over time, mean SBP and DBP over time, and incidence of and frequency of eye symptoms and other adverse events will be summarized by treatment group. The incidence of AEs by seriousness, severity, body system, preferred term and relatedness to study drug will be summarized by treatment group.

Mean and frequency distribution of changes from baseline through Day 15 in HR, SBP and DBP will be provided by treatment group and by each method measured. The frequency of participants with $\geq 25\%$ increase in HR, decrease in SBP, decrease in DBP vs. baseline as measured with any of the methods will be provided by treatment group. The mean and frequency distribution of percentage of days with $\geq 25\%$ increase in HR, decrease in SBP, decrease in DBP vs. baseline will be provided by treatment group. The mean and median RR, QRS, QT, QTcF values from ECG will be provided by treatment group.

The mean change in HR, SBP and DBP from Day 1 to Days 4, 7, 10, 14 and 15 will be provided by treatment group and by each method measured. The change in frequency of participants with eye symptoms (all, severe, serious) and abnormal visual acuity and abnormal color vision scores from Day 1 to Days 4, 7, 10, 14 and 15 will be provided by treatment group. The mean change in HR, SBP and DBP from screening to Days 28 and 42, and from Day 14 to Days 28 and 42 will be provided by treatment group and by each method measured. The change in frequency and duration of eye symptoms (all, severe, serious) and/or abnormal visual acuity and/or abnormal color vision scores from screening to Days 28 and 42, and from Days 1-14 (combined) to Days 28-42 (combined) will be provided by treatment group.

The mean, median and range of each blood/serum and urine safety parameter at screening, Day 3, Day 7, Day 14 and Day 42 will be provided by treatment group. The mean, median and range of the changes in each blood/serum and urine safety parameter from screening to Day 3, Day 7, Day 14 and Day 42 will be provided by treatment group. Changes may be assessed on the raw (difference) or log (fold change) scale, depending on the whether the distribution of the measure is more appropriately described by a normal or lognormal distribution, respectively.

Bayesian linear and nonlinear mixed effects models will be utilized to characterize the profile of continuous variables (e.g., heart rate, blood pressure) over time, and the proportion of patients in the population reaching clinically relevant thresholds will be estimated. From these models, the likelihood of tachyphylaxis can be characterized by the posterior probability that the mean heart rate decreases from Day 1 to Day 14, the posterior probability that the mean blood pressure on decreases from Day 1 to Day 14, and the posterior probability that the frequency of patients with eye symptoms (all, severe, serious) decreases from Day 1 to Day 14.

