2.3. Benefit/Risk Assessment

In this trial patients with untreated, drug-sensitive pulmonary TB will receive for 14 days either the test drug TBA-7371 in 1 of 5 regimens (from 100 mg QD to 400 mg QD) or commercial HRZE fixed combination (Rifafour® e-275) as control drug, dosed as recommended in the package insert.¹

HRZE is a first line treatment for drug sensitive TB with a well-established, generally favorable, yet not straightforward, benefit-risk profile. The most common AEs associated with HRZE are peripheral neuropathy, optic neuritis, hepatitis, and gastro-intestinal AEs (see Package Insert¹ and 2018 Safety Update² enclosed in study specific manual(s)).

TBA-7371 was tested in adult healthy volunteers in 1 clinical trial (TBA7371-001), composed of three parts: a single ascending dose (SAD) part where single doses from 100 to 800 mg were

tested, a multiple ascending dose (MAD) part where 100, 200 and 400 mg QD were taken for 14 days and a drug-drug interaction (DDI) part. The most common treatment-emergent adverse events (TEAEs) were increase in heart rate associated with decrease in blood pressure and eye symptoms (blurred vision, photophobia, altered color vision, increased lacrimation). The frequency of such events was dose related, starting at doses above 100 mg /day. Most were mild and transient. In particular, vision-related AEs were of short duration, resolved before the next dose and were not persistent changes. Furthermore, tachyphylaxis to changes in heart rate and blood pressure appeared to occur in the MAD part of the trial.

The eye symptoms appeared to be associated with C_{max} . It is therefore possible that the tolerability profile could improve with fractionation of the daily dose. This justifies the inclusion of the BID and TID dosing regimens in this trial.

There is no information on the efficacy of TBA-7371 in humans. PK/PD modelling from animal experiments, supplemented with additional PK data from healthy human subjects, suggests that bactericidal effect could be present at 100 mg/day and then increase with dose.

More information on TBA-7371 is provided in the Investigator Brochure.

The overall risks associated with TBA-7371 at or below 400 mg QD are considered low and are mitigated by the following design features of the present protocol:

- throughout the 14-day Treatment Phase eye symptoms, visual acuity and color vision, ECG will be assessed/recorded every 3-4 days, vital signs daily;

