The scientific rationale for secondary endpoints is as follows:

- EBA as assessed by alternative methods [TTP in MGIT culture and LAM assay]. MGIT culture and LAM assay are easier to conduct compared to solid media culture. Hence, insight into the suitability of such methods to replace solid media culture will be useful for this and other TB drug development programs.
- Full AE assessment. All AE will be assessed by seriousness, intensity (severity), relationship to study drug and expectedness based on the information provided in the

Investigator Brochure and summarized by body system and preferred medical term. This will allow the full safety and tolerability profiling of TBA-7371.

- Assessment of heart rate and blood pressure via vital signs and ECG, eye symptoms, visual acuity and color vision. These measurements were selected based on the safety profile that emerged from animal studies and from phase 1 study TBA7371-001 (see above). Multiple assessment methods will be carried out for cardiovascular variables to maximize the sensitivity of the study. Eye symptoms will be assessed by non-leading questions delivered by trained staff based on a standardized script. Visual acuity and color vision will be assessed through standardized procedures. The possibility of decrease (tachyphylaxis) or increase over time of these unwanted effects, as well as their persistence or recurrence in the month following discontinuation of study drug, will also be assessed: results of study TBA7371-001 suggest changes over time during treatment with TBA-7371 of cardiovascular (decrease) and eye (increase) adverse events. It should be noted that all eye symptoms reported study TBA7371-001 were transient.

PK profile and relationship between exposure and magnitude of EBA. So far, the PK profile of TBA-7371 has been only studied in animals and in healthy volunteers. This study allows the confirmation of the PK profile in TB patients. The relationship between exposure and bactericidal response will guide the selection of the dose regimen(s) for further development of TBA-7371. No active metabolite of TBA-7371 has been identified so far, and no major metabolite seen in humans has been detected at more than 10% of parent TBA-7371. Therefore, TBA-7371 metabolism will not be examined further in this study.

Additional measurements may be added as exploratory endpoints. Exploratory endpoints will be the object of separate documents.

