10.2.5. Definition of AESI

Adverse events of special interest (AESIs) are adverse events that the sponsor wants to monitor carefully and which are subject to expedited reporting (within 24 hours) from the investigator to the Sponsor or representative following the same process and timelines than the SAEs.

In this trial the following AEs will be collected and reported as AESI:

- Anaphylactic reaction
- \geq Grade 2 intensity (severity) and/or serious AE related to increase of heart rate (HR);
- \geq Grade 2 intensity (severity) and/or serious AE related to decrease of SBP;
- \geq Grade 2 intensity (severity) and/or serious AE related to decrease of DBP;
- \geq Grade 2 intensity (severity) and/or serious eye symptom-related AE.

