8 CHANGES IN CONDUCT / RE-LANNED ANALYSES FROM THE PROTOCOL

No changes have been made to the planned analyses.

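### The protocol's posterior-probability criterion for tachyphylaxis points the wrong way for blood pressure, and the SAP neither corrects nor withdraws it

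*Protocol*

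**What the plan says.** Tachyphylaxis for heart rate, SBP, DBP and eye symptoms is a stated secondary safety objective (Protocol 3.2; SAP 5.2). Protocol 9.4.2.2 plans Bayesian mixed-effects models for the continuous safety variables. It says that from these "the likelihood of tachyphylaxis can be characterized by the posterior probability that the mean heart rate decreases from Day 1 to Day 14". It adds a matching probability for BP, "the posterior probability that the mean blood pressure on decreases from Day 1 to Day 14", and a third for the frequency of participants with eye symptoms. All three are worded as decreases. No time of day is given.

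Protocol 2.3 gives the direction of the drug effect in Phase 1: "increase in heart rate associated with decrease in blood pressure and eye symptoms". Protocol 4.2 gives the meaning of the term: "The possibility of decrease (tachyphylaxis) or increase over time of these unwanted effects".

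The SAP contains no Bayesian model for vital signs and no posterior probability of tachyphylaxis. It describes BP changes by treatment group (SAP 6.4, 12.5.1, 12.5.2). SAP Section 8 states: "No changes have been made to the planned analyses".

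**The concern.** Heart rate goes up on the drug and BP goes down, yet one verb serves both. Tolerance to an effect that raises a variable is a later fall. Tolerance to an effect that lowers a variable is a later rise. An analyst who programs the BP clause as written would report a high probability of tachyphylaxis when the post-dose fall is growing, and a low one when it is wearing off.

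Phase 1 suggested that tolerance to the heart-rate and BP changes does occur (Protocol 2.3). If that repeats, the written rule would report almost none of it for BP. What is at stake is the answer to one secondary safety objective.

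**Working it through.** The documents attach no number to this criterion, so there is no figure to reproduce. The check is one of sign, followed by an illustration.

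**Sign check**

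- *Drug effect on BP: negative.* Source: Protocol 2.3.
- *Harm direction for BP: a fall.* Protocol 9.4.2.2 counts participants with a change of 25% or more in the harmful direction: "increase in HR, decrease in SBP, decrease in DBP vs. baseline as measured with any of the methods will be provided by treatment group". Protocol 10.2.5 lists among the adverse events of special interest, at Grade 2 or above, "intensity (severity) and/or serious AE related to decrease of SBP", with a parallel entry for DBP.
- *Tachyphylaxis: the unwanted effect becomes smaller.* Source: Protocol 4.2.

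| Variable | Drug effect | Tolerance, Day 1 to Day 14 | Criterion as written | Agrees? |
|---|---|---|---|---|
| Heart rate | up | down | decreases | yes |
| Eye symptom frequency | up | down | decreases | yes |
| Mean BP, post-dose | down | up | decreases | no |

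**Illustration**

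The group size of 15 is from Protocol 4.1. Everything else is assumed: a Day 1 post-dose effect of −10 mmHg, stable pre-dose BP, an SD of within-person change of 8, 10 or 12 mmHg, a flat prior and a normal posterior. With d the observed mean change in post-dose BP from Day 1 to Day 14:

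P(decrease) = Φ(−d / (SD/√15)), and P(increase) = 1 − P(decrease).

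The standard errors are 8/√15 = 2.07, 10/√15 = 2.58 and 12/√15 = 3.10 mmHg.

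| Scenario | d (mmHg) | P(decrease), SD 8 / 10 / 12 | P(increase), SD 8 / 10 / 12 |
|---|---|---|---|
| Tolerance: −10 to −5 | +5 | 0.008 / 0.026 / 0.053 | 0.992 / 0.974 / 0.947 |
| No change | 0 | 0.500 / 0.500 / 0.500 | 0.500 / 0.500 / 0.500 |
| Worsening: −10 to −15 | −5 | 0.992 / 0.974 / 0.947 | 0.008 / 0.026 / 0.053 |

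The sizes depend on the assumptions. The reversal does not: on post-dose values the two probabilities are complements.

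**Which reference value**

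The reversal needs a Day 1 value taken after dosing. The SAP sets the Day 1 reference before the first dose (SAP 6.4 and 9.2). Change from that value shows whether an effect is present. Neither a rise nor a fall from it measures loss of effect.

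**Was the rule withdrawn?**

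The SAP's record of Amendment 2 reports the replacement of a Bayesian model only under SAP 11.1.3, the CFU sensitivity analysis. The one Bayesian safety analysis left in the SAP is optional and concerns eye symptoms (SAP 12.2). Nothing addresses the vital-sign models.

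**The case against.** The case against giving this much weight is substantial.

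- **It looks like a slip.** The BP clause is ungrammatical, so a word may be missing, and the rest of the protocol treats a BP fall as the effect and as the harm. It would be wrong to infer that the sponsor holds a considered view that falling BP means tolerance. This stands as an explanation. It does not remove the error, because the text names mean BP and a decrease, and no other section corrects it.
- **The SAP does not carry the analysis.** SAP 12.5.1 tabulates pre-dose and post-dose BP and same-day changes on Days 1, 4, 7, 10 and 14, and SAP 12.5.2 tabulates daily values. Both would show the true direction. This stands and limits the consequence.
- **A reader might infer that worsening hypotension would be missed or a safety conclusion reversed.** The documents do not support that. The probability is something the protocol says can be used to characterize tachyphylaxis, with no threshold, success criterion or link to escalation. Falls of 25% or more, orthostatic falls (SAP 12.5.3), adverse events of special interest and the IDMC's review of vital signs (Protocol 9.7.1) all capture BP falls with the right sign.
- **A reader might also infer that the inference is reversed whatever data are used.** The clause names no time point, and the reversal holds only for post-dose values.

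The objection does not show that the rule has gone. Protocol 10.1.7 says changes to the analyses belong in the SAP, and SAP Section 8 says there are none.

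**Conclusion.** The BP direction in Protocol 9.4.2.2 is wrong as written; the heart-rate and eye-symptom directions are right. This follows from the protocol's own statements and needs no numerical assumption. If the criterion is run on post-dose values, it scores a deepening fall as tolerance and a recovery as no tolerance. The figures of 0.947 to 0.992 and 0.008 to 0.053 only illustrate this and rest on the assumed effect and SDs.

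The consequence is limited to one secondary objective, with no decision attached and with descriptive tables that would expose the discrepancy. It still deserves correction. As the documents stand, either the analysis is run with the wrong sign, or it is dropped while the SAP says that nothing changed.

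**What to change.** Make one SAP entry, choosing between two routes.

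1. **Keep the analysis.** State the BP criterion as the posterior probability that the post-dose fall in SBP, and separately in DBP, is smaller on Day 14 than on Day 1. Define the fall as the change from same-day pre-dose at a named time, such as 2.5 h. The Bayesian vital-sign model must then also be specified, since the SAP has none.
2. **Withdraw it.** Record in SAP Section 8 that the Bayesian vital-sign tachyphylaxis analysis is dropped, and name as its replacement the Day 14 versus Day 1 comparison of the intraday post-dose changes in SAP 12.5.1. The comparison has to be named because SAP 12.5.1 summarizes each day on its own, and change from Day 1 pre-dose does not measure loss of effect.

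Under either route, show pre-dose BP on Days 1 and 14 beside the result (already in SAP 12.5.2). A Day 14 pre-dose value that still carries drug effect would make the same-day fall look smaller without tolerance.

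The second route costs a few lines of SAP text and a little programming; the first also needs the model written out. Neither needs new data, since the pre-dose and post-dose readings on both days are already scheduled. Protocol 10.1.7 lets the SAP carry the change.

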9.5. PK Analyses

Concentration data will be summarized by treatment group using nominal time points. Individual and mean concentration versus nominal time plots will be presented by treatment groups. PK parameters will be summarized by treatment group.

The relationship of each TBA7371 PK parameter (AUC, C_{max} , T>MIC) and CFU counts (e.g. BA_{CFU}(0-14), CFU change) will be explored graphically for the treatment groups combined. The PK and CFU data used in the correlations will also be presented in tabular format. If a correlation

is observed, further analysis may be performed to identify exposure targets for response. Details of such analysis will be provided in the analysis plan.

9.6. Demographic and Compliance Analyses

Demographic parameters (age, sex, and race/ethnicity) and other baseline characteristics will be summarized by treatment group for all participants in the safety population.

Listings of randomized participants with protocol deviations (to be defined in the SAP) will be presented by treatment group.

9.7. Interim Analyses

No formal interim analysis is planned in this trial.

Unmasked safety and (if available) PK data on each cohort will be provided to the IDMC.

9.7.1. Independent Data Monitoring Committee (IDMC)

The independent IDMC will be established to oversee the safety of this study and to make a go / no-go decision at each dose escalation step.

The IDMC will operate according to a charter. The IDMC structure, participants and other details will be provided in the charter. The charter will be available prior to study start.

The IDMC will review unmasked safety and, if available, PK data during regular scheduled safety review meetings. The IDMC may request additional information, or a pause in recruitment and study treatment, while safety data are being evaluated.

During active enrollment, the IDMC will meet at least once before each of the 3 dose escalation steps, unless a decision is made to stop recruitment earlier. The IDMC reviews will include vital signs, ECG and eye symptoms / visual acuity and color vision tests, and safety laboratory tests as well as solicited and unsolicited AE and SAE. All procedures associated with these reviews, including objectives, data handling, elements included for review, and recommendations will be documented.

The IDMC will make a formal recommendation on the continued enrolment into the trial after each safety review.

The IDMC charter will provide meeting information and other details.

If study drug administration is paused by the local medical monitor or the principal investigator, the IDMC will convene on an ad hoc basis.

The recommendation of the IDMC, along with the sponsor's decision, will be communicated to the investigators and the IRB/IEC and the national regulatory authorities as required. The sponsor or its designee agrees to abide to any directives issued by the national regulatory authority of the IRB.

10. Supporting Documentation and Operational Considerations

10.1. Appendix 1. Regulatory, Ethical, and Study Oversight Considerations

10.1.1. Regulatory and Ethical Considerations

This study will be conducted in accordance with the protocol and with the following:

- Consensus ethical principles derived from international guidelines including the Declaration of Helsinki and Council for International Organizations of Medical Sciences (CIOMS) International Ethical Guidelines
- Applicable International Council for Harmonization of Technical Requirements for Pharmaceuticals for Human Use (ICH) Good Clinical Practice (GCP) Guidelines
- Applicable laws and regulations
- The protocol, protocol amendments, ICF, and other relevant documents (e.g., diary cards) must be submitted to an IRB/IEC by the investigator and reviewed and approved by the IRB/IEC before the study is initiated.
- Any amendments to the protocol will require IRB/IEC approval before implementation of changes made to the study design, except for changes necessary to eliminate an immediate hazard to study participants.

10.1.2. Study Oversight

The study sponsor, the IRB/IEC, the institution through which the research is performed, and all members of the principal investigator's clinical team and the national regulatory authority share responsibility for ensuring the safety of participants in this trial.

The principal investigator will be responsible for the following:

- Providing written summaries of the status of the study to the IRB/IEC annually or more frequently, in accordance with the requirements, policies, and procedures established by the IRB/IEC
- Notifying the IRB/IEC of SAEs or other significant safety findings as required by IRB/IEC procedures
- Providing oversight of the conduct of the study at the site and adherence to requirements of ICH and GCP guidelines, SAHPRA Regulations the IRB/IEC, and all other applicable country and local regulations.
- Closely monitoring study participants and taking whatever measures necessary to ensure their safety. The principal investigator may delay an individual's study drug administration or pause study drug administration altogether if the investigator is concerned that the study drug might place a participant or participants at significant risk. Where specified, the responsibilities of the principal investigator may be delegated to a medically qualified team member (designee). The investigator determines severity and causality with respect to the study drug for each AE.

The sponsor has an institutional responsibility to ensure participant safety and is ultimately accountable for safety oversight. Local medical monitors and the IDMC play an important role in this regard and support the sponsor.

The local medical monitor is the sponsor's representative and is a physician or surgeon in their country of residence. The local medical monitor:

- reviews the safety of the product for protocols in a specific region and, in conjunction with the sponsor, determines expectedness of AEs.
- Is responsible for safety oversight in-country and plays an important role in the reporting of SAEs, ADRs and pregnancies, as described in the protocol
- in consultation with the sponsor, may assess the severity and causality for AEs and may upgrade the degree of severity and causality determined by the principal investigator or designee

The IRB or EC has institutional responsibility for the safety of research participants. The IRB or EC has the authority to terminate, suspend or require changes to a clinical trial.

The national regulatory authority, SAHPRA, has the authority to terminate, suspend or require changes to a clinical trial.

